### 3 Tables

**Table 1** *Accrual by centre*

Centre	Number of accrual (%)		
	SBRT N = ***	CRT N = ***	Total N = ***
XXXX	XX (XX)	XX (XX)	XX (XX)

**Table 2:** *Accrual by Stratification Factors at Randomization*

Data set: All Randomized Patients			
	Number of patients (%)		
	SBRT N = ***	CRT N = ***	Total N = ***
Histology :			
radioresistant	** (**)	** (**)	** (**)
radiosensitive	** (**)	** (**)	** (**)
“Mass”* on imaging			
Present	** (**)	** (**)	** (**)
Absent	** (**)	** (**)	** (**)

Source: Centralized Randomization File

**Table 3: Stratification factor at randomization vs. at baseline**

Data set: All Randomized Patients			
	Number of patients (%)		
At randomization	At baseline	SBRT N = ***	CRT N = ***
Histology			
radioresistant	radioresistant	** (**)	** (**)
radioresistant	radiosensitive	** (**)	** (**)
radiosensitive	radioresistant	** (**)	** (**)
radiosensitive	radiosensitive	** (**)	** (**)
“Mass”* on imaging			
Present	Present	** (**)	** (**)
Present	Absent	** (**)	** (**)
Absent	Present	** (**)	** (**)
Absent	Absent	** (**)	** (**)

**Table 4: Treatment received vs. Treatment randomized to receive**

Data set: All Randomized Patients			
	Number of Patients (%)		
	Randomized Arm		
	SBRT N=***	CRT N=***	Total N=***
Treatment Received			
SBRT	*** (**)	*** (**)	*** (**)
CRT	*** (**)	*** (**)	*** (**)
Not treated	*** (**)	*** (**)	*** (**)

**Table 5: Eligibility status and Major Protocol Violations**

Total patients allocated	SBRT N = ***	CRT N = ***	Total N = ***
Ineligible	XX (XX)		
Total eligible patients	XX (XX)		
REASONS FOR INELIGIBILITY			
Reason 1	XX (XX)		
Reason 2	XX (XX)		
Major Protocol Violations			
XXX			
XXX			

**Table 6: Summary of Follow-up**

Data set: All Randomized Patients			
	Number of patients		
	CRT N = ***	SBRT N = ***	Total N = ***
Median	***	***	***
Min	**	**	**
Max	**	**	**

**Table 7: Patient characteristics**

All randomized patients	SBRT N = ***	CRT N = ***	Total N = ***
AGE			
<=39	XX (XX)		
40-49	XX (XX)		
50-59			
60-69			
>=70	XX (XX)		
Median (Range)	XX (XX)		
Gender			
M			
F			
Primary Malignancy			
ECOG performance status			
Number of consecutive Spinal segments in target volume			
Worst pain score at baseline			
Prior spinal surgical/diagnostic procedures for cancer			
Y			
N			
Prior radiation therapy to their spine for cancer (Y vs N)			
SINS score (Median, min, max; mean, std, Also by categories: 0-6 vs 7 -12 vs 13 – 18)			

Opioid medications reported in the last 24 hours			
Epidural Disease Extent (Bilsky scale)			

**Table 8: Baseline signs and symptoms**

Data set: All Randomized Patients (SBRT Arm)						
	Number of patients (%)					Any grade
	N=***					
	Worst grade					
	NR	1	2	3	4	
Patients with any sign/symptom at baseline	** (**)	** (**)	** (**)	** (**)	** (**)	** (**)
Patients with particular sign or symptom, within body system:						
Body System 1 	** (**)	** (**)	** (**)	** (**)	** (**)	** (**)
Event 1	** (**)	** (**)	** (**)	** (**)	** (**)	** (**)
Event 2	** (**)	** (**)	** (**)	** (**)	** (**)	** (**)
Event 3	** (**)	** (**)	** (**)	** (**)	** (**)	** (**)
...	** (**)	** (**)	** (**)	** (**)	** (**)	** (**)
Body System 2 	** (**)	** (**)	** (**)	** (**)	** (**)	** (**)
Event 1	** (**)	** (**)	** (**)	** (**)	** (**)	** (**)
...	** (**)	** (**)	** (**)	** (**)	** (**)	** (**)
	** (**)	** (**)	** (**)	** (**)	** (**)	** (**)

(1) Patients may have more than one event within a body system

**NOTE: Same table to be made for CRT Arm**

**Table 9: Baseline Concomitant Medications**

Data set: All Randomized Patients			
	Number of patients (%)		
	SBRT N=***	CRT N=***	Total N=***
Any concomitant medication at baseline 			
No	** (**)	** (**)	** (**)
Yes	** (**)	** (**)	** (**)

 Any con meds taken within 24 hours prior to the Day 0 treatment assessment

**Table 10: Baseline Cancer Treatment**

Data set: All randomized Patients			
	Number of patients		
	SBRT N = ***	CRT N = ***	Total N = ***
Yes	** (**)	** (**)	** (**)
No	** (**)	** (**)	** (**)
Unknown	** (**)	** (**)	** (**)

**Table 11: Reasons for in-evaluable for Pain Response**

Data set: All Randomized Patients			
Reasons for inevaluable for Pain response	Number of patients		
	SBRT N = ***	CRT N = ***	Total N = ***
***	***	***	***
***	**	**	**
***	**	**	**

**Table 12: Complete pain response at 3-month after treatment (ITT)**

Data set: All Randomized Patients			
Response Status	Number of patients		
	SBRT N = ***	CRT N = ***	Total N = ***
CR	***	***	***
PR	***	***	***
SD	***	***	***
PD	***	***	***
Inevaluable	***	***	***

**Table 12b: Complete pain response at 3-month after treatment (per protocol and evaluable patients)**

**Table 13: Cochran Mantel Haenszel and Logistic Regression Model for Complete response rate 3-month post treatment**

Data set: All Randomized Patients

Treatment/ Prognostic Factc	Univariate Analysis 		Multivariate Analysis 	
	Odds Ratio (95%CI)	CMH p-vlaue	Odds Ratio (95% C.I.	p-value from logisti regression
Treatment arm SBRT : CRT	**.* (**.*; **.*	0.***	**.* (**.*; **.*	0.***
Prognostic factor 1 Level 1: level 2	NC 	0.***	**.* (**.*; **.*	0.***
Prognostic factor 2 Level 1: level 2	NC	0.***	**.* (**.*; **.*	0.***
Prognostic factor 3 Level 1: level 2	NC	0.***	**.* (**.*; **.*	0.***
... ...	NC	0.***	**.* (**.*; **.*	0.***

(1) Stratified by stratification factors  
 (2) Stratified Logistic regression, all factors included  
 (3) NC = not computed  
 (4) Odds ratio of first category over second category

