4.0 TRIAL DESIGN

4.1 Stratification

Patients will be stratified by:

1. Histology (radioresistant[♦] vs. radiosensitive[♦])
2. “Mass”^{*} on imaging (present vs. absent)
3. Centre

- ♦ radioresistant are renal cell carcinoma, melanoma, sarcoma and gastro-intestinal; radiosensitive are all other types
- * refers to tumour that involves the paraspinal tissues or presence of epidural disease (extra osseous disease extension)

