#### 2.4.1.5 Patient Characteristics (Table 7)

- Age: 0-39, 40-49, 50-59, 60-69, 70+, median, min and max;
- Gender (M VS F)
- Primary malignancy (Breast, Lung, GI, GU, Gyn, ...)
- ECOG performance status (0, 1, 2)
- Number of consecutive Spinal segments in target volume (1, 2, 3)
- Worst pain score at target treatment site at baseline (median, min and max)
- Prior spinal surgical/diagnostic procedures for cancer (Y vs N).
- Prior radiation therapy to their spine for cancer (Y vs N).
- SINS score (Median, min, max; mean, std, also by categories: 0-6 vs 7 -12 vs 13 – 18), Epidural Disease Extent (Bilsky scale) (1, 1a, 1b, 1c, 2, 3 ..)
- SINS score by categories of Location, Pain, Bone Lesion, Radiographic Spinal Alignment, Vertebral Body Collapse, and Posterolateral Involvement. (Median, min, max; mean, std).
- Angular Kyphosis (degrees) (0, 1, 2...),
- Opioid medications reported in the last 24 hours (Median, min and Max, mean, std)
- bisphosphonates or other bone targeted therapy ( Y vs. N).

\*An unknown category will be added when appropriate.

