### **2.5.2.1 Complete pain response at 3-month post treatment**

Patients will be considered to achieve a complete pain response if they meet the criteria for complete pain response outlined in 2.5.1.1.

A table of number of patients who were not evaluable for the primary endpoint of complete pain response will be provided by treatment arm. (Table 11).

A table of number of patients meeting the primary endpoint of complete pain response at 3-month after treatment start by arm will be provided. (Table 12).

The complete pain response rate is defined as number of patients achieved complete pain response / number of patients randomized for each treatment arm. Chi-square analysis will be applied to test the complete pain response rate between the two arms and the 95% confidence interval of the rate difference (SBRT arm – CRT arm) between the two arms will be calculated. The Cochran-Mantel-Hanzeal Chi-square will be used to test the difference in the complete pain response rate stratified by stratification factors at randomization except of study center. P-value from Chi-square test without adjustment for the stratification factors will also be provided for sensitivity.

Logistic regression will be used to assess the relationship between complete pain response incidence and the following factors (Table 13):

- Treatment arm
- Age (as a continuous variable and/or as a categorical variable: below and above median);
- Gender
- Primary Malignancy
- ECOG performance status
- Worst pain score at baseline
- SINS score.

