**Table 19: Log rank and Cox Regression Model for Radiation site Progression Free Survival**

Data set: All Randomized Patients					
		Univariate Analysis 		Multivariate Analysis 	
Treatment Arm/ Prognostic Factors ; Baseline	Median PFS (Months)	Hazard Ratio  (95% CI)	Log-ran p-vlaue	Hazard Ratio  (95% C.I.)	P-vlaue from Cox regression
Treatment arm			†0.***		0.***
SBRT	***	***		***	
CRT	***	(***, ***)		(***, ***)	
Prognostic factor 1			0.***		0.***
Level 1	***	NC 		***	
Level 2	***			(***, ***)	
Prognostic factor 2			0.***		0.***
Level 1	***	NC		***	
Level 2	***			(***, ***)	
Prognostic factor 3			0.***		0.***
Level 1	***	NC		***	
Level 2	***			(***, ***)	
...			0.***		0.***
...	***	NC		***	
...	***			(***, ***)	

(1) Stratified  
(2) Stratified Cox regression with all factors included  
(3) NC = not computed  
(4) Hazard ratio of first category over second category

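### Tumour type is fitted in a logistic model already stratified by histology, so odds ratios that cross the radioresistant/radiosensitive line are non-estimable or only indirect

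*SAP*

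**What the plan says.** SAP 2.5.2.1 introduces the model with "Logistic regression will be used to assess the relationship between complete pain response incidence and the following factors (Table 13" and lists treatment arm, age, gender, "Primary Malignancy", ECOG status, baseline worst pain and SINS. The Table 13 footnotes describe the univariate column as "Stratified by stratification factors" and the multivariate column as "Stratified Logistic regression, all factors included". They define each ratio as "Odds ratio of first category over second category". Tables 15 and 17 carry the same footnotes, for the 6-month endpoint (SAP 2.5.2.2) and for overall pain response. In the univariate column only the treatment row has an odds ratio; the prognostic factors get a CMH p-value. Any tumour-type odds ratio therefore comes from the multivariate column.

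SAP 2.3 gives the adjustment strata as histology and mass. Protocol 4.1 defines histology: "radioresistant are renal cell carcinoma, melanoma, sarcoma and gastro-intestinal; radiosensitive are all other types". The malignancy categories in SAP 2.4.1.5 start "Primary malignancy (Breast, Lung, GI, GU, Gyn" and are left open. The SAP does not say where renal cell carcinoma is coded, and it does not mention that malignancy and histology overlap.

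Protocol 14.2 gives logistic regression two tasks: an adjusted treatment effect and an exploratory search for predictors of complete response.

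**The concern.** A stratified model compares patients within strata. With strata recorded correctly, GI patients are always in the radioresistant stratum, and breast, lung and gynaecological patients are in the radiosensitive one. A GI-versus-breast ratio therefore has no within-stratum data behind it. Depending on how malignancy is coded, the software will either drop a level or print a number that depends on a third category. Neither the row label nor the footnote tells the reader which has happened.

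What is at stake is the tumour-type row of an exploratory table. Tumour type is an obvious candidate predictor of response to radiation, and the contrast of most interest, resistant against sensitive types, is the one that fails.

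**Working it through.** **The plan's own figure.** With 17% vs 34%, two-sided 5%, 80% power and a continuity correction, the standard two-proportion formula gives 114 per arm, or 228, as stated. The point does not depend on this figure.

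**Case 1: each category lies in one stratum.** Take six types: breast, lung and prostate (sensitive), and GI, renal and melanoma (resistant). The design has an intercept, a histology term and five malignancy indicators, so 7 columns. Its rank is 6, because the histology column equals the sum of the three resistant-type indicators. One contrast is aliased. No ratio across the histology line can be estimated, while ratios within a group can.

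**Case 2: renal and other GU share one GU category.** The design has 6 columns and rank 6, so everything can be fitted. Write a0 and a1 for the sensitive and resistant intercepts, with breast as reference:

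- logit(breast) = a0
- logit(prostate) = a0 + GU
- logit(renal) = a1 + GU
- logit(GI) = a1 + g

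Solving gives g = [logit(GI) − logit(renal)] + [logit(prostate) − logit(breast)]. The printed GI:breast odds ratio is therefore (GI:renal) × (prostate:breast). The direct ratio is this multiplied by renal:prostate, a factor that the stratum term absorbs. With only histology and malignancy in the model, this large-sample result does not depend on the tumour mix.

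**Numbers.** The documents give no response by tumour type, so all rates below are assumptions, chosen to show a range. Odds are p/(1 − p), and products use unrounded values.

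| Set | Breast | Prostate | GI | Renal | Direct GI:breast | GI:renal | Prostate:breast | Printed GI:breast |
|---|---|---|---|---|---|---|---|---|
| A | 35% | 30% | 10% | 12% | 0.21 | 0.815 | 0.796 | 0.65 |
| B | 30% | 30% | 15% | 15% | 0.41 | 1.00 | 1.00 | 1.00 |
| C | 30% | 35% | 12.5% | 25% | 0.33 | 0.43 | 1.26 | 0.54 |
| D | 30% | 40% | 15% | 10% | 0.41 | 1.59 | 1.56 | 2.47 |

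Set A in full: direct = (0.10/0.90)/(0.35/0.65) = 0.206; printed = 0.815 × 0.796 = 0.65; and 0.65 × renal:prostate 0.318 returns 0.206.

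Lung:breast lies within one stratum. With lung at 30%, 25% and 20% in sets B, C and D, it is 1.00, 0.78 and 0.58 with or without the histology term.

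**Effect on the treatment estimate.** I used 500 simulated trials of 228 patients allocated 1:1. The assumed mix was breast 25%, lung 25%, prostate 15%, GI 12%, renal 18% and melanoma 5%, with GU pooled and GI merged with melanoma. Tumour type acted only through histology (−0.5 resistant, +0.25 sensitive on the logit scale, around 17% on CRT). The arm log odds ratio was 0.92, which is ln[(0.34/0.66)/(0.17/0.83)]. Mass was left out for simplicity. Medians:

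| Model | Treatment log OR (SE) | GI/melanoma vs breast log OR (SE) |
|---|---|---|
| Stratified, with malignancy | 0.965 (0.328) | −0.04 (0.80) |
| Stratified, without malignancy | 0.953 (0.323) | – |
| Not stratified by histology, with malignancy | 0.958 (0.326) | −0.78 (0.53) |

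The simulated direct value for GI/melanoma vs breast is −0.5 − 0.25 = −0.75. The model without histology recovers it with a smaller standard error, and the treatment estimate hardly moves.

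**The case against.** The strongest defence is that the stratified row is not a biased estimate of the direct ratio. It is a different estimand, a histology-adjusted odds ratio, and the footnote does say that the model is stratified. Pooling GU does not force renal and other GU tumours to have equal response either, because they can differ through the two stratum intercepts. In the two-factor example the fitted model reproduces every cell. All of this stands. It does not answer the labelling problem: a reader who takes "Odds ratio of first category over second category" at face value will read the row as GI against breast, and under the other coding there is no such row.

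A reader might infer several stronger things that the documents do not support:

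- **All tumour-type ratios are wrong.** They are not; ratios within a histology group keep their meaning. The stratified CMH p-value for malignancy is a valid test within strata, though not an overall test of tumour type.
- **The distortion always hides a difference.** Set D reverses the direction. Table 14 also shows response by histology and arm, so a difference between the two groups would still be visible there.
- **Hazard ratios are affected.** Tables 19 and 22 say only "Stratified Cox regression with all factors included" and show placeholder factors. Neither SAP 2.5.2.3 and 2.5.2.5 nor Protocol 14.6 names malignancy as a Cox covariate.
- **The primary result is compromised.** The primary CMH test compares arms and does not include malignancy.

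Exact nesting would also fail if strata were misrecorded at randomization, which Table 3 is designed to detect, or if another category, such as a mixed group for remaining sites, held both histology groups. Cross-group ratios would then be identified through those patients, which is no more interpretable.

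**Conclusion.** The point holds for the exploratory tumour-type rows of Tables 13, 15 and 17. Followed as written, the SAP gives cross-histology odds ratios that are either not estimable or are indirect contrasts carrying a plain label. That structure follows from the documents alone. The size does not: direct versus printed values of 0.21 vs 0.65, 0.41 vs 1.00, 0.33 vs 0.54 and 0.41 vs 2.47 rest on assumed rates and on renal cell being coded under GU, and they show that both size and direction depend on unknown quantities. The treatment odds ratio is practically unchanged (log odds ratio 0.965 vs 0.958 in simulation), and the primary CMH test and the 228 patients are untouched. Tables 19 and 22 are affected only if malignancy is later chosen as a Cox covariate. This is a modest but real flaw that is cheap to remove.

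**What to change.** In Tables 13, 15 and 17, keep the stratified logistic model for the treatment effect but leave primary malignancy out of it. Report tumour type from one additional exploratory logistic model with arm, mass and the other listed covariates, without histology. In that model, code renal cell separately from other GU and merge sparse sites by a rule fixed before the analysis. Such a rule is needed because the planned rates imply only about 114 × (0.17 + 0.34) = 58 responders.

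Alternatively, keep the strata, state the malignancy coding including where renal cell sits, and report only contrasts within a histology group.

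In either case, name the Cox covariates for Tables 19 and 22, and apply the same rule there if malignancy is among them.

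The cost is some SAP wording and, for the first option, one extra exploratory model. Tumour type and histology would then no longer appear in the same model.

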**Table 14: Complete Response rate at 3-month after treatment According to Baseline Stratification Factors**

Data set: All Randomized Patients			
Number of Responses/Number of Patients (%)			
	SBRT N=***	CRT N=***	Int-P-value
Histology			0.**
radioresistant	**/** (**)	**/** (**)	
radiosensitive	**/** (**)	**/** (**)	
l“Mass”* on imaging			0.**
Present	**/** (**)	**/** (**)	
Absent	**/** (**)	**/** (**)	

**Table 15: Cochran Mantel Haenszel and Logistic Regression Model for Complete response rate 3 months post treatment**

Data set: All Randomized Patients				
Treatment/ Prognostic Factc	Univariate Analysis 		Multivariate Analysis 	
	Odds Ratio (95%CI)	CMH p-vlaue	Odds Ratio (95% C.I.	p-value from logisti regression
Treatment arm SBRT : CRT	**.* (**.* , **.*	0.***	**.* (**.* , **.*	0.***
Prognostic factor 1 Level 1: level 2	NC 	0.***	**.* (**.* , **.*	0.***
Prognostic factor 2 Level 1: level 2	NC	0.***	**.* (**.* , **.*	0.***
Prognostic factor 3 Level 1: level 2	NC	0.***	**.* (**.* , **.*	0.***

...	...	NC	0.***	** ** (** ***,** *)	0.***
-----	-----	----	-------	------------------------	-------

(1) Stratified by stratification factors  
 (2) Stratified Logistic regression, all factors included  
 (3) NC = not computed  
 (4) Odds ratio of first category over second category

**Table 16: Complete Response rate 3-month after treatment According to Baseline Stratification Factors**

Data set: All Randomized Patients			
Number of Responses/Number of Patients (%)			
	SBRT N=***	CRT N=***	Int-P-value
Histology			0.**
radioresistant	**/** (**)	**/** (**)	
radiosensitive	**/** (**)	**/** (**)	
l"Mass"* on imaging			0.**
Present	**/** (**)	**/** (**)	
Absent	**/** (**)	**/** (**)	

**Table 17: Cochran Mantel Haenszel and Logistic Regression Model for Response rate 3-month post treatment**

Data set: All Randomized Patients				
Treatment/ Prognostic Fact	Univariate Analysis 		Multivariate Analysis 	
	Odds Ratio (95%CI)	CMH p-vlaue	Odds Ratio (95% C.I.	p-value from logisti regression
Treatment arm		0.***		0.***
SBRT : CRT	** ** (** ***,** *)		** ** (** ***,** *)	
Prognostic factor 1		0.***		0.***
Level 1: level 2	NC 		** **	

			(**.**.,**.**)	
Prognostic factor 2		0.***		0.***
Level 1: level 2	NC		**.**.	
			(**.**.,**.**)	
Prognostic factor 3		0.***		0.***
Level 1: level 2	NC		**.**.	
			(**.**.,**.**)	
...		0.***		0.***
...	NC		**.**.	
			(**.**.,**.**)	

- (1) Stratified by stratification factors  
(2) Stratified Logistic regression, all factors included  
(3) NC = not computed  
(4) Odds ratio of first category over second category

**Table 18: Response rate 3-month after treatment According to Baseline Stratification Factors**

Data set: All Randomized Patients			
Number of Responses/Number of Patients (%)			
	SBRT	CRT	Int-P-value
	N=***	N=***	
Histology			0.**
radioresistant	**/** (**)	**/** (**)	
radiosensitive	**/** (**)	**/** (**)	
“Mass”* on imaging			
Present	**/** (**)	**/** (**)	0.**
Absent	**/** (**)	**/** (**)	

**Table 19: Log rank and Cox Regression Model for Radiation site Progression Free Survival**

Data set: All Randomized Patients					
		Univariate Analysis 		Multivariate Analysis 	
Treatment Arm/ Prognostic Factors ; Baseline	Median PFS (Months)	Hazard Ratio  (95% CI)	Log-ran p-vlaue	Hazard Ratio  (95% C.I.)	P-vlaue from Cox regression
Treatment arm			†0.***		0.***
SBRT	***	***		***	
CRT	***	(***, ***)		(***, ***)	
Prognostic factor 1			0.***		0.***
Level 1	***	NC 		***	
Level 2	***			(***, ***)	
Prognostic factor 2			0.***		0.***
Level 1	***	NC		***	
Level 2	***			(***, ***)	
Prognostic factor 3			0.***		0.***
Level 1	***	NC		***	
Level 2	***			(***, ***)	
...			0.***		0.***
...	***	NC		***	
...	***			(***, ***)	

(1) Stratified  
(2) Stratified Cox regression with all factors included  
(3) NC = not computed  
(4) Hazard ratio of first category over second category

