12.3 Follow-up Off Protocol Treatment

All patients will be followed until 6 months after the end of radiotherapy.

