14.3 Sample Size and Duration of Study

For the randomized phase II portion of the study, a convenience sample size of 54 patients is considered sufficient to evaluate whether accrual is feasible. This sample size would also provide an opportunity to estimate the CRT and SBRT 3 month complete pain relief response rates, which would provide the basis for the sample size calculation of the future randomized controlled trial. We chose a sample size that provides for standard error rates in both treatment arms to be less than 10%. Assuming that the CRT response rate is 10% to 30%, with 27 patients, the standard error for the estimated response rate will be 5.8% to 8.8%, respectively. Assuming that the SBRT response rate is about 30% to 50%, with 27 patients, the standard error for the estimated response rate would be 8.8% to 9.8%, respectively.

The trial was activated in July 2015. By November 2016, 44 patients had been enrolled onto the study and the accrual rate indicated that the sample size would be reached in 18 months, thereby meeting the primary objective of the phase II feasibility study. Other metrics of trial conduct were examined including treatment related toxicity and tolerability as well compliance with radiotherapy including quality assurance measures. No safety signals were detected in either arm. Notably, spinal fracture within the treatment fields occurred in 2 patients - both on the conventional treatment arm (CRT). Compliance with protocol mandated radiotherapy and quality assurance measures was high.

Based on the demonstration of feasibility of trial conduct and continued need to critically evaluate the efficacy of SBRT in the treatment of painful spinal metastases, approval was sought and granted in January 2017 for conversion of the study design from a randomized phase II feasibility study to a randomized phase II/III study comparing the two radiotherapy treatment strategies.

Sample size estimate for the phase III controlled trial is with a two-sided 5% level test and 80% power. Based on the results of a randomized phase II trial [*Sprave 2018*] with similar enrollment and radiobiology criteria as the current study, we estimate the complete pain responses will be 20% for the CRT and 40% for the SBRT treatment arms, respectively.

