Assuming a 15% drop out/inevaluable rate, we expect the complete pain response rates for the intent-to-treat analysis to be 17% and 34% for the CRT and SBRT arms, respectively. The sample size for the phase III study is 228. Multiple sensitivity analyses will also be performed to further evaluate the results: (i) complete case analysis that excludes those with missing/inevaluable; (ii) multiple imputation analysis that assigns different portions of those missing/inevaluable to be either responders or non-responders. A secondary “as treated” sensitivity analysis will be performed to include only eligible patients who have received protocol-assigned radiation therapy.

Table: Sample Size Parameters for a Subsequent Randomized Controlled Trial

| CRT response | SBRT response | Effect size | Drop-out rate | Total Sample Size |
|--------------|---------------|-------------|---------------|-------------------|
| 10 | 30 | 20 | 0.1 | 160 |
| 10 | 30 | 20 | 0.05 | 152 |
| 15 | 35 | 20 | 0.1 | 186 |
| 15 | 35 | 20 | 0.05 | 176 |
| 20 | 40 | 20 | 0.1 | 206 |
| 20 | 40 | 20 | 0.05 | 194 |
| 25 | 45 | 20 | 0.1 | 220 |
| 25 | 45 | 20 | 0.05 | 210 |
| 30 | 50 | 20 | 0.1 | 230 |
| 30 | 50 | 20 | 0.05 | 218 |
| 10 | 25 | 15 | 0.1 | 252 |
| 10 | 25 | 15 | 0.05 | 238 |
| 15 | 30 | 15 | 0.1 | 298 |
| 15 | 30 | 15 | 0.05 | 284 |
| 20 | 35 | 15 | 0.1 | 338 |
| 20 | 35 | 15 | 0.05 | 320 |
| 25 | 40 | 15 | 0.1 | 370 |
| 25 | 40 | 15 | 0.05 | 350 |
| 30 | 45 | 15 | 0.1 | 392 |
| 30 | 45 | 15 | 0.05 | 372 |

This table shows potential sample sizes for the planned RCT study with two-sided alpha = 0.05 and power = 80%. The sample size is very sensitive to the CRT response rate. For example, for an effect size of 20%, if the response rate with CRT is 10%, the sample size will be 160 patients while if the response rate is 30%, the sample size will increase to 230.

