14.6 Secondary Endpoint and Analysis

Complete pain response in the treatment area at 6 months post-radiation. All analyses for the primary endpoint will be performed for the complete pain response at 6 months post-radiation.

AMEND #1: 2017-FEB-02; AMEND #2: 2018-APR-03; AMEND #3: 2018-OCT-31

Radiation site progression-free survival (RSS PFS) is defined as the time from the date of randomization to the date of documented local progression, as defined in Section 10.2.2; or the date of death. Patients who have not progressed or died by the cutoff date of final analysis, RSS PFS will be censored on the date of the last disease assessment. A Kaplan-Meier curve for proportions of RSS PFS in each treatment arm will be displayed. The RSS PFS rates at 3 and 6 months and their 95% confidence intervals will be estimated. The 95% confidence intervals for the medial RSS PFS will be computed using the method of Brookmeyer and Crowley. The difference in distributions of RSS PFS in the two treatment arms will be compared using the log-rank test stratified by the stratification factors at randomization except study centre. Other potential important factors that predict RSS PFS will be assessed using Cox regression. Overall survival will be analysed similarly.

The incidence of acute severe adverse incidences for each arm will be calculated with its 95% confidence interval, and the analyses will be performed in a tiered comparison, i.e., comparing the overall incidence rates between treatment arms first, then comparison of radiotherapy and disease related symptoms and compared by means of Chi-square analysis or Fisher exact test.

SINS scores will be summarized for data at baseline, 3 and 6 months evaluations. The potential prognostic effects of baseline SINS score on the complete pain response at 3 months post-radiation and the overall survival will be explored using logistic and Cox regression models respectively.

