### **2.5.1.4 Radiation site progression-free survival (RSS PFS) at 3 and 6 months**

Radiation site progression free survival is defined as the time from randomization to local progression or death. For patients who did not reported progression of disease and alive will be censored at the last disease evaluation time. It is based on the center investigator reported data.

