**Table 20: Radiation site Progression Free Survival by Subsets**

Data set: All Randomized Patients							
Factors	Value	N	SBRT		CRT		P-value Interactio
			Median RSS PFS 95% C.I.	N	Median RSS PFS 95% C.I.	Hazard Ratio  95% C.I.	
Histology	Radioresistant	**	** ** (** ***, ** ***)	**	** ** (** ***, ** ***)	** ** (** ***, ** ***)	0.***
	Radiosensitiv e	**	** ** (** ***, ** ***)	**	** ** (** ***, ** ***)	** ** (** ***, ** ***)	
“Mass” ** on imaging	Present	**	** ** (** ***, ** ***)	**	** ** (** ***, ** ***)	** ** (** ***, ** ***)	0.***
	Absent	**	** ** (** ***, ** ***)	**	** ** (** ***, ** ***)	** ** (** ***, ** ***)	

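### The planned median RSS PFS is unreliable: progressions and clean-scan censorings share the last MRI cluster, so a spurious median of about 6.5–7.5 months may be printed

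*SAP*

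**What the plan says.** RSS PFS runs from randomization to local progression or death (protocol 10.2.2 and 14.6; SAP 2.5.1.4). A patient without progression who is "alive will be censored at the last disease evaluation time". Protocol 14.6 has the same rule.

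Spine MRI after treatment is scheduled only at 3 and 6 months, counted from the end of radiotherapy (protocol 9.1 and Appendix I). Radiotherapy may start up to 3 weeks after randomization (protocol 5.1.11 and 8.0). No window is set for the MRI; SAP 2.9.2.1 sets windows for the quality-of-life forms only. Data collection then stops: "All patients will be followed until 6 months after the end of radiotherapy" (protocol 12.3), and Appendix IV says that later deaths are not recorded.

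Medians are nevertheless planned. Table 19 has "Median PFS (Months" by arm and prognostic-factor level. Table 20 has "Median RSS PFS" with a 95% CI by stratum. Protocol 14.6 says that "95% confidence intervals for the medial RSS PFS will be computed using the method of Brookmeyer and Crowley" (evidently a slip for median). Neither document has a rule for interval censoring, for dating scans to nominal visits, or for withholding a median when few patients remain at risk.

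**The concern.** At the second MRI each remaining patient becomes either an event or, if clean, a censored observation on that same day. These days differ between patients when counted from randomization. As early-scanned clean patients leave, each later progression is divided by a smaller number still unscanned. Censoring here coincides with the inspection that reveals the event, so those still unscanned do not stand for those already found clean. The curve keeps falling through the cluster and can cross 50% for reasons unrelated to the true median. Missed visits are not needed for this.

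At stake are a printed summary for each arm, factor level and subset, its confidence interval, and the tail of Figure 1. One arm could show a false value near 7 months beside an arm marked as not reached, which would misstate the contrast.

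**Working it through.** **The plan's own figure.** The documents give no expected RSS PFS rate, median, event count or power. The only design figure to reproduce is the sample size, which supplies the arm size. Protocol 14.3 sizes phase III "with a two-sided 5% level test and 80% power"; "we expect the complete pain response rates for the intent-to-treat analysis to be 17% and 34" per cent; "The sample size for the phase III study is 228".
- Uncorrected n per arm = [1.96·√(2×0.255×0.745) + 0.8416·√(0.17×0.83 + 0.34×0.66)]² / 0.17² = 102.0, so 103 per arm, 206 in total.
- With continuity correction: (102.0/4)·[1 + √(1 + 4/(102.0×0.17))]² = 113.5, so 114 per arm, 228 in total. Reproduced.

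**Inputs.** From the protocol: local control of about 45% at one year with conventional treatment, stated for bulky tumours (2.1), and about 80% with SBRT, no time point given (2.2; read here as one year). Assumed: 10% deaths by 6 months, constant hazards, radiotherapy ending about 0.5 month after randomization, progression dated at the MRI. Second scans then centre on 6.5 months.

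**Closed form.** Let p be the proportion progressing between the two scans, S the curve just before the second cluster, and f the fraction of that cluster not yet scanned. Each scan multiplies the curve on average by about 1 − p/k with k patients left. The product is about S·f^p, where the correct end value is about S·(1 − p).

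At 45% control:
- p = 1 − 0.45^(3/12) = 0.181.
- S = 0.45^(3.5/12) × 0.90 = 0.792 × 0.90 = 0.71.
- Crossing 0.5 requires f^0.181 = 0.5/0.71 = 0.704, so f is about 0.14. That is about 11 of the 114 × 0.71 = 81 patients reaching the scan.
- True event-free proportion at 6.5 months: 0.45^(6.5/12) × 0.90^(6.5/6) = 0.58.
- True median: ln 2 / (0.0665 + 0.0176) = 8.2 months.

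At 80% control, p = 1 − 0.80^(3/12) = 0.054, the true event-free proportion is 0.79 and the true median 19 months. The average curve does not reach 0.5, but a progression in the last patient scanned sends it to zero and one in the second-last halves it. These two routes alone give about 2 × 0.054 = 11%.

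**Simulation, 114 per arm, 10% deaths.** Ranges are across runs with different scan-date spread and radiotherapy-start assumptions.

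| One-year local control | Trials printing a median |
|---|---|
| 45% | about 93–95% |
| 60% | about 60–70% |
| 70% | about 35–40% |
| 80% | about 16–20% |

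At 45% control (scan-date SD 0.25 month) the mean curve is 0.63 at 6.5, 0.50 at 6.75 and 0.34 at 7.0 months and ends at 0.25, against true values of 0.58, 0.57 and 0.56 at those three times. About 12–13 of 114 patients are at risk at the printed median; at 80% control, 2–3.

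A second set of runs, indexed by the crude event-free share of the arm, printed a median in 96–97% at about 59%, 80–86% at 63%, 59–70% at 66%, 43–50% at 69%, 23–34% at 75% and 4–12% at 83–90%. Typical values were 6.7–7.4 months. With 30 per arm, as in a Table 20 subset, the figures at 10% deaths are 72–78% (45% control) and 15–19% (80% control).

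**Check of the remedy.** With all second-scan results at one common time, the 45% curve ends at 57.9% against a true 57.9%, and a median is printed in 2–7% of trials. With each patient's own due date counted from randomization and no visit slack, a median is still printed in about 93%: the permitted variation in radiotherapy start is enough.

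**The case against.** A reader might infer that every printed median will be an artefact of about 6.7 months. The documents do not support that. They give no 6-month progression or death rate, and the result turns on both. The 45% figure is for bulky tumours, while the trial enrols patients with and without a mass and stratifies on it; applying it to the whole CRT arm is an upper case. At 80% control most trials would print not reached. The value also shifts with the assumed delay and scan spread. All of this stands.

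A reader might also take the median as the headline result. It is not. The named endpoint is RSS PFS at 3 and 6 months. SAP 2.5.2.3 plans those rates with their variance by arm, plus a stratified log-rank test and a hazard ratio; protocol 14.6 adds confidence intervals for the rates. The between-arm comparison is therefore not missing, although Tables 19 and 20 have no column for the rates or their difference. Nor was it examined here whether the log-rank test or hazard ratio is disturbed, so nothing is claimed against them.

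Finally, the planned interval would give some warning. When a median was printed, its upper limit was not reached in about 65% of CRT-type runs and in essentially all SBRT-type runs. That is only partial protection, since the point estimate would still be printed.

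**Conclusion.** The concern holds as a conditional risk. Assessment schedule, time origin, censoring rule and end of follow-up together make the Kaplan-Meier median of RSS PFS unreliable. It may print about 6.5–7.5 months although more than half the arm is event-free. This is very likely at 45% one-year local control, more likely than not at 60%, and a minority outcome at 70–80%, with 114 per arm and 10% deaths. Where an arm is already near 50% before the 6-month scans, the median is largely genuine. The conclusion assumes that progression is dated at the MRI and that event-free patients are censored at their own last scan. It concerns a descriptive summary of a secondary endpoint and should be corrected; it does not touch the primary analysis.

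**What to change.** In SAP Tables 19 and 20 and protocol 14.6, replace the median and its confidence interval with RSS PFS at the 3- and 6-month visits by arm, with 95% CIs, and the SBRT minus CRT difference with its 95% CI. Estimate these in one of two ways:
- place every patient's scan result, progression or clean, at one common analysis time per visit, count events before censorings at ties, and end the curve at the 6-month visit; or
- use an interval-censored estimator.

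State explicitly that the common time is the same for all patients. Each patient's own due date counted from randomization leaves the artefact in place. Keep the stratified log-rank test and the hazard ratio.

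The cost is SAP and protocol wording and a little programming on data already collected. The downside is that no median is reported, including where one would have been largely genuine.
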